### **7.6.1 Deaths**

Deaths are listed for enrolled subjects without regard to study period. The listing includes treatment regimen, death date, start and end date of dosing, source of information, and cause of death. Deaths from multiple sources of information are identified:

- Subject status: study discontinuation reason of death;
- AE/SAE: MedDRA higher level, lower level or preferred term contains ‘death’; SAE outcome of death; SAE category of death; death date.

Deaths are also summarized without regard to study period for treated subjects for the following categories: total; due to AE.

### **7.6.2 Other Serious Adverse Events**

Pre-treatment SAEs are summarized by treatment regimen for enrolled subjects (ETV, PBO, not treated). Pre-treatment SAEs are those that occurred prior to the first dose of study therapy.

SAEs are also summarized by treatment regimen for the following cohorts and study periods:

- Through Week 48 on blinded therapy for treated subjects
- After Week 48 on blinded therapy or on open-label ETV through Week 96 for the Year 2 Safety Cohort
- On ETV treatment for the All ETV Safety Cohort
- Off-treatment follow-up for off-treatment follow-up subjects in the Post-Year 1 Safety Cohort
- Long-term follow-up for long-term follow-up subjects in the Post-Year 1 Safety Cohort
- Alternative ETV follow-up for alternative ETV follow-up subjects in the Post-Year 1 Safety Cohort.

SAEs leading to death and SAEs related to study therapy and leading to death are also summarized analogously during the on-treatment period for the 3 cohorts.

Multiple on-treatment SAEs (all; related to study therapy) are also summarized for the 3 cohorts, presenting the numbers of events and exposure-adjusted incidence rates (see [Section 8.10](#)).

### **7.6.3 Adverse Events Leading to Discontinuation of Study Therapy**

AEs leading to discontinuation of study therapy are summarized by treatment regimen for the following cohorts and study periods:

- Through Week 48 on blinded therapy for treated subjects
- After Week 48 on blinded therapy or on open-label ETV through Week 96 for the Year 2 Safety Cohort
- On ETV treatment for the All ETV Safety Cohort

### **7.6.4 Other Significant Adverse Events**

#### **7.6.4.1 Events of HBV Disease Progression**

Events of HBV disease progression are summarized by treatment regimen for treated subjects across the on-treatment and long-term follow-up periods combined (see Table 7.6.4.1-1).

---

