## 4.3 Other Secondary Endpoints

- The number and percent of subjects with adverse events (including palatability issues), serious adverse events (SAEs), discontinuations due to adverse events, and HBV disease progression through Week 48;
- Proportions of subjects with HBeAg loss at Weeks 48 and 96;
- Proportion of subjects with HBeAg seroconversion at Week 96;
- Proportion of subjects who maintained HBeAg seroconversion at Week 96 (end of blinded therapy) among subjects who achieved HBeAg seroconversion at Week 48;
- Histological analysis among subjects with available liver biopsy.

[REDACTED]

- [REDACTED]

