## 7 STATISTICAL ANALYSES

### 7.1 General Methods

All analyses (efficacy, safety and PK) are presented by treatment regimen, ie, ETV vs PBO, based on the appropriate cohort and dataset defined in the earlier section. For Week 48 analysis, all the endpoints are to be cut off through Week 48, unless specified otherwise.

The PK analyses are described in [Section 7.7](#). The methods described below are used to analyze safety and efficacy data.

Categorical variables are summarized either with counts and percents or with proportions (number with event divided by number evaluable) and percents, depending on the endpoint.

Continuous variables are summarized with univariate statistics (eg, n, mean, median, standard deviation, standard error, quartiles, minimum, and maximum).

Longitudinal analyses of efficacy and safety parameters use pre-defined visit week windows (see [Section 8.4](#)). Windows around planned measurement times are constructed based on the

midpoint between planned measurement visits unless specified otherwise. Data are summarized at each scheduled visit through the analysis week.

Analyses of HBV DNA use values only from the central laboratory from the Roche COBAS® TaqMan HBV Test with limit of quantitation (LOQ) of 29 IU/mL and limit of detection (LLD) of 10 IU/mL.

Analyses of laboratory tests and serology use values from the central or local laboratory. Laboratory parameters are summarized using US standard values and units. Refer to [Section 8.11](#) for conversion of select laboratory test values from the Abbott Architect system to the Roche Diagnostics Hitachi Modular system.

Formats of tables, listings and graphs are described in the Data Presentation Plan (DPP).

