## **7.6 Safety**

The investigators determine the intensity of AEs and the relationship of AEs to study therapy. The investigators' terms are coded and grouped by system organ class using the latest version of the Medical Dictionary for Regulatory Activities (MedDRA) in production at BMS.

In order to account for AEs with multiple occurrences in the same subject, AE records are collapsed for each subject and preferred term when records have the same onset date, or when records are contiguous or overlapping (see [Section 8.10](#)). All AE presentations are based on collapsed records.

AEs are presented by system organ class and preferred term, both in descending order of incidence on ETV, unless specified otherwise.

AE presentations include both non-serious and SAEs as defined in the protocol, unless specified otherwise. If a subject had an AE with different intensities during the study period, then only the greatest intensity is reported.

On-treatment safety is assessed for the following 3 cohorts (see [Sections 6.1](#) and [6.3](#)):

- Through Week 48 on blinded therapy for treated subjects
  - ETV and PBO are assessed on treatment up to the Week 48 cut, ie, the earlier of (a) 54 weeks, the upper bound of the Week 48 visit window (see [Section 8.4](#)), and (b) the first dose of open-label ETV.
- After Week 48 on blinded therapy or on open-label ETV through Week 96 for the Year 2 Safety Cohort

- ETV, PBO BL and PBO OL are assessed on treatment after the Week 48 cut and up to 102 weeks, the upper bound of the Week 96 visit window (see [Section 8.4](#)).
- On ETV treatment for All ETV Safety Cohort

Note that AEs with onset on the first day of study therapy are considered on treatment, AEs with onset on the first day of ETV are considered on ETV treatment and AEs with onset on the first day of open-label ETV are considered on open-label ETV.

Follow-up safety is assessed for the following 3 cohorts (see [Sections 6.1](#) and [6.3](#)):

- During off-treatment follow-up for off-treatment follow-up subjects in the Post-Year 1 Safety Cohort
- During long-term follow-up for long-term follow-up subjects in the Post-Year 1 Safety Cohort.
- During alternative ETV follow-up for alternative ETV follow-up subjects in the Post-Year 1 Safety Cohort (select endpoints only).

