### 7.6.5 Overall Adverse Events

AEs are summarized by intensity (All Grades; All Grades related; Grade 2 - 4 related; Grade 3 - 4) and treatment regimen for the following 3 cohorts:

- Through Week 48 on blinded therapy for treated subjects
- After Week 48 on blinded therapy or on open-label ETV through Week 96 for the Year 2 Safety Cohort
- On ETV treatment for the All ETV Safety Cohort

If relationship to study therapy is missing, the AE is included in summaries of AEs related to study therapy.

AEs are also summarized by intensity (All Grades) and treatment regimen during (1) off-treatment follow-up for off-treatment follow-up subjects in the Post-Year 1 Safety Cohort, (2) alternative ETV follow-up for alternative ETV follow-up subjects in the Post-Year 1 Safety Cohort, and (3) long-term follow-up for long-term follow-up subjects in the Post-Year 1 Safety Cohort.

On-treatment non-serious AEs (All Grades) occurring with incidence  $\geq 5\%$  on any treatment regimen are also summarized analogously for the 3 cohorts. Multiple on-treatment non-SAEs (All Grades) occurring with incidence  $\geq 5\%$  on any treatment regimen are also summarized for the 3 cohorts, presenting the numbers of events and exposure-adjusted incidence rates (see [Section 8.10](#)).

Multiple on-treatment AEs (All Grades) occurring with incidence  $\geq 5\%$  on any treatment regimen are also summarized for the 3 cohorts, presenting the numbers of events and exposure-adjusted incidence rates (see [Section 8.10](#)).

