### **7.6.8 Results by Subgroups**

The following key safety endpoints are summarized by subgroups of age randomization strata, geographic region, HBV genotype and route of transmission (see [Section 7.5.1](#)) on blinded therapy through Week 48 for treated subjects, unless specified otherwise:

- SAEs
- AEs leading to discontinuation of study therapy
- Events of HBV disease progression (on-treatment and long-term follow-up periods combined)
- AEs by intensity (All Grades; Grade 2 - 4 related; Grade 3 - 4)
- Laboratory abnormalities by toxicity grade (Grade 1 - 4; Grade 3 - 4)
- Select laboratory elevations and abnormalities
- Growth/development assessment values and changes from baseline over time (on-treatment and long-term follow-up periods combined). Tanner stage is assessed only by age randomization strata for each staging category (see [Section 7.6.7](#)).

AEs are presented by system organ class and preferred term alphabetically.

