## 9 CONTENT OF REPORTS

The primary analysis is conducted when the Primary Cohort has been treated for 48 weeks (see Section 6.3). Longitudinal analyses present data on treatment through Week 48. Efficacy is focused on the Primary Cohort. Safety is focused on blinded therapy through Week 48 for treated subjects, as well as on all ETV therapy for the All ETV Safety Cohort. Follow-up safety is presented only if ≥ 10% of treated subjects have post-dosing follow-up data.

An additional analysis is performed when all subjects have reached Week 48. Longitudinal analyses present efficacy data on treatment through Week 48 for treated subjects, efficacy data on treatment through Week 96 for the Year 2 Primary Efficacy Cohort, safety data on treatment through Week 96 for the Year 2 Safety Cohort, and all available safety data on ETV treatment for the All ETV Safety Cohort. All safety analyses described in this plan are performed.

An additional unplanned analysis is performed when all subjects have reached Week 96. All analyses described in this plan are performed, except for pre-treatment analyses of study population and efficacy/safety analyses on blinded therapy through Week 48.

An additional analysis is performed when all subjects have completed study therapy. All analyses described in this plan are performed, except for pre-treatment analyses of study population, efficacy/safety analyses on blinded therapy through Week 48, and efficacy/safety analyses on treatment through Week 96.

The final analysis is performed when the last subject has completed long-term follow-up. At a minimum, safety analyses are reported for the off-treatment and long-term follow-up periods.

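### SAP 7.6.4.1 and 7.6.8 summarise HBV disease progression only over treatment and long-term follow-up pooled, so no section specifies the through-Week-48 subject count listed in SAP 4.3

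*SAP*

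**What the plan says.** SAP 4.3, like Protocol 8.3 and the synopsis, lists one safety endpoint with four parts. It ends with "discontinuations due to adverse events, and HBV disease progression through Week 48".

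The dedicated analysis, SAP 7.6.4.1, uses a different window: it summarises these events by regimen, among treated subjects, "across the on-treatment and long-term follow-up periods combined". The subgroup section, SAP 7.6.8, starts from a default of blinded therapy to Week 48 and then exempts this item by name: "Events of HBV disease progression (on-treatment and long-term follow-up periods combined".

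Table 7.6.4.1-1 defines progression as any of ten MedDRA preferred terms among serious and non-serious AEs.

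Three other provisions bear on the point:

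- SAP 7.1: "For Week 48 analysis, all the endpoints are to be cut off through Week 48, unless specified otherwise".
- SAP 9, on the primary analysis: "Safety is focused on blinded therapy through Week 48 for treated subjects".
- SAP 7.6.5, whose first period for AE tables is "Through Week 48 on blinded therapy for treated subjects".

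**The concern.** The randomised, blinded comparison of ETV with placebo effectively ends at Week 52, when children without HBeAg seroconversion in either arm go to open-label ETV. A progression count by arm that runs past that point compares ETV with a column made up of placebo, then ETV, then post-treatment follow-up. It no longer answers the question posed by an endpoint that stops at Week 48.

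Events are likely to be few, because Protocol 4.2.2 excludes children with a history of variceal bleeding, encephalopathy or treated ascites. That is an inference; the documents give no rate. With small counts, one event after the switch that is counted under placebo could change how the table reads.

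**Working it through.** **1. The four parts of the endpoint, side by side**

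| Part (SAP 4.3) | Analysis section | Table for blinded therapy to Week 48? |
|---|---|---|
| Adverse events | SAP 7.6.5 | Yes |
| Serious adverse events | SAP 7.6.2 | Yes |
| Discontinuations for AEs | SAP 7.6.3 | Yes |
| HBV disease progression | SAP 7.6.4.1, 7.6.8 | No; pooled periods only |

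**2. Who is in the placebo column**

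SAP 6.2 groups safety results as treated. A child leaves the randomised group only if the wrong therapy was taken for the whole treatment period, so a placebo child who switches at Week 52 remains in placebo. SAP 6.3 does define cohorts that separate placebo children who did and did not receive open-label ETV, but 7.6.4.1 is written for treated subjects by regimen and does not use them. The long-term follow-up period in SAP 6.1 runs to the end of the study and does not stop at alternative anti-HBV therapy. In Protocol 8.4.2, off-treatment follow-up does stop there.

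**3. Follow-up after Week 48 at the primary analysis**

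Inputs (SAP 5): the first 123 subjects accrue evenly over 2 years, and the last placebo subject completes Week 48 by study week 144. Counting a year as 48 weeks reproduces the SAP's figure: 2 × 48 + 48 = 144.

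- Earliest subject: 144 − 48 = 96 weeks after Week 48; 96 / 144 = 67%.
- Mean follow-up, even accrual and no dropout: (48 + 144) / 2 = 96 weeks. Time after Week 48: 96 − 48 = 48 weeks. Share of total person-time: 48 / 96 = 50%.
- With 52-week years, the range is 48 to 152 weeks. The maximum share is 104 / 152 = 68%. Mean follow-up is 100 weeks and the share is 52 / 100 = 52%.

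These figures cover the first 123 subjects. Any subject enrolled later would have less than 48 weeks at that date and would lower the average.

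**4. The placebo column over the whole study**

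SAP 5 assumes 10% HBeAg seroconversion on placebo. Its own step reproduces: 18 × 0.9 = 16.2, given as 16 switching. Among placebo children who reach Week 48, ignoring dropout:

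- Mean blinded placebo time = 0.9 × 52 + 0.1 × 96 = 56.4 weeks.
- Share of the 264-week study = 56.4 / 264 = 21%.

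Most of the placebo column's time in the final version of this table is therefore open-label ETV or post-treatment follow-up.

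**5. What the Week 48 AE tables supply**

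Under SAP 7.6, "AEs are presented by system organ class and preferred term, both in descending order of incidence on ETV". Each of the ten terms is thus a row by arm for blinded therapy to Week 48. Rows cannot be added into subjects, because a child with both ascites and varices is in two of them. For each arm they give only bounds: at least the largest row, at most the sum of the rows. They also cover on-treatment time only, which SAP 6.1 ends 5 days after the last dose. An event before Week 48 in a child who had already stopped is therefore outside them.

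**The case against.** A reader might infer that the blinded comparison of progression is never produced. The documents do not support that. Progression events are AEs by definition, so every on-treatment component is visible by arm in the Week 48 tables. What is not specified is the count of subjects with any component.

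It can also be argued that SAP 7.1 and 7.6.4.1 work together: 7.6.4.1 says which periods are pooled, 7.1 then cuts the pooled data at Week 48 for the Week 48 analysis, and SAP 9 points the same way. That reading is possible, but 7.1 yields to any section that sets its own period. 7.6.4.1 does so, and the bracketed exemption in 7.6.8 looks deliberate. SAP 9 states a focus and creates no progression table. A programmer following 7.6.4.1 would build the pooled table. Table layouts are in a Data Presentation Plan that is not among the documents; it may contain the missing count, but the SAP does not require it.

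Two further points stand. Pooling treatment and follow-up is a reasonable display for rare, late events, and SAP 7.6.4.2 does the same for malignant neoplasms, so the pooled table should stay. And a strictly on-treatment Week 48 table would not match the endpoint either. SAP 4.3 says through Week 48 without limiting it to time on therapy, and Protocol Figure 5.3.2.1 (note 5) moves children given rescue ETV straight into long-term follow-up, so an on-treatment cut would lose their later events.

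**Conclusion.** The point holds as a mismatch between a listed endpoint and its specified analysis. The pooled summaries do not estimate progression through Week 48, and the component rows in the AE tables do not amount to the subject-level count.

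At the primary analysis, about half of the first 123 subjects' follow-up lies after Week 48, assuming even two-year accrual and no dropout. Two thirds is the maximum, for the earliest subjects, and should not be read as typical. These are shares of follow-up time; they are not an estimate of bias, and the documents give no event rate from which to derive one.

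Nor should the mismatch be read as a threat to the trial's inference. The endpoint is a descriptive number and percent outside the testing sequence of SAP 7.5, so sample size, power and alpha are untouched. It is still worth correcting, because the stated rule gives a different quantity from the one listed and the correction is small.

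**What to change.** In SAP 7.6.4.1, and in the subgroup list in 7.6.8, add the number and percent of treated subjects, by arm, with any Table 7.6.4.1-1 term up to the Week 48 cut. Use the cut in SAP 7.6: the earlier of 54 weeks from first dose and the first open-label ETV dose.

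State that events before the cut are counted in subjects who stopped blinded therapy early. SAP 8.9 leaves rescue ETV out of the dose-date derivations, so the text should confirm that starting rescue does not itself end the count. A footnote should say that AE collection is narrower after study drug stops (Protocol 6.3.2 and Table 6.1, note e).

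Keep the pooled table as a second display, labelled as including open-label ETV and post-treatment time.

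The cost is one table and its subgroup version, built from data already collected and a cut rule already defined.

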**Table 7.6.4.1-1: Events of HBV Disease Progression**

---

**Serious and non-serious AEs: preferred terms in MedDRA dictionary**

Ascites, Gastric varices, Gastric varices haemorrhage, Hepatic cirrhosis, Hepatic encephalopathy, Hepatic neoplasm malignant, Hepatorenal syndrome, Oesophageal varices haemorrhage, Peritonitis bacterial, Varices oesophageal

---

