Procedure	Screening ≤ 6 Weeks prior to Randomization	Randomize Initiate study drug (Day 1) within 72 hours	On Study Treatment Weeks 4, 8, 12 ± 3 days, and every 12 weeks ± 5 days up to end of study drug dosing	Weeks 52, 100 and 148 ± 10 days (if needed)^a	End of Treatment (Scheduled or Early)	Observational LTFU^b Weeks 6, 12, and every 12 weeks ± 5 days Up to 264 weeks total study participation [or 48 weeks beyond completion of rescue open- label ETV used for treatment of an extreme elevation of ALT due to acute exacerbation of CHB; whichever is later]	Protocol Section
Serious Adverse Events Assessment	X	X	X		X	X	6.3
Concomitant Medication Use	X	X	X		X		5.5
Use of anti-HBV therapies						X	5.5
Assess HBV related diagnoses						X	7.3
Hematology, Chemistry (4 - 5.5 mL) ^f	X	X	X		X	X	6.9
INR (1.8 mL)	X	X	Week 24 and every 24 weeks		X	Week 24 and every 24 weeks	6.9

Table 6.1: Flow Chart for Protocol AI463189

Procedure	Screening ≤ 6 Weeks prior to Randomization	Randomize Initiate study drug (Day 1) within 72 hours	On Study Treatment Weeks 4, 8, 12 ± 3 days, and every 12 weeks ± 5 days up to end of study drug dosing	Weeks 52, 100 and 148 ± 10 days (if needed)^a	End of Treatment (Scheduled or Early)	Observational LTFU^b Weeks 6, 12, and every 12 weeks ± 5 days Up to 264 weeks total study participation [or 48 weeks beyond completion of rescue open- label ETV used for treatment of an extreme elevation of ALT due to acute exacerbation of CHB; whichever is later]	Protocol Section
HIV Serology (1 mL)	X		Weeks 48, 96 and 144 ^g		X	Weeks 48 and 96 after initiation of rescue open- label ETV ^d	6.9
Pregnancy Test ^h	X	X	X		X	X ⁱ	7.6
Efficacy Assessments							
Hepatitis B serologies (1 mL)	X	X	Week 12 and every 12 weeks		X	Week 24 and every 24 weeks	6.9
HBV DNA PCR (2 mL)	X	X	Week 4, Week 12 and every 12 weeks		X	Weeks 6, 12, 24, and every 24 weeks	6.9
HBV Genotype (HBV subtype) (2 mL)		X					6.9

Table 6.1: Flow Chart for Protocol AI463189

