Procedure	Screening ≤ 6 Weeks prior to Randomization	Randomize Initiate study drug (Day 1) within 72 hours	On Study Treatment Weeks 4, 8, 12 ± 3 days, and every 12 weeks ± 5 days up to end of study drug dosing	Weeks 52, 100 and 148 ± 10 days (if needed) ^a	End of Treatment (Scheduled or Early)	Observational LTFU ^b Weeks 6, 12, and every 12 weeks ± 5 days Up to 264 weeks total study participation [or 48 weeks beyond completion of rescue open- label ETV used for treatment of an extreme elevation of ALT due to acute exacerbation of CHB; whichever is later]	Protocol Section
Specimens for Resistance Testing (3 mL)		X	Week 48, 96, 144 ^j		X		6.9
Other Assessments							
Sparse PK (2 ml) ^k			Weeks 4, 12, 24, 48				
Semi-intensive PK (8 ml) ^l			Week 4				
Clinical Drug Supplies							
Dispense Study Medication		X	X	X		X ^d	5.2
Assessment of Study Medication Use			X	X	X	X ^d	5.6

- ^a Assessments of seroconversion will be made based on serology results at Weeks 48, 96, and 144. Study drug will be modified, continued, or discontinued according to the study schema (Section 4.1).
- ^b Only protocol required visits and assessments are mentioned. Subjects placed on rescue open-label ETV to treat an extreme elevation of ALT due to acute exacerbation of CHB should undergo additional non-protocol visits and assessments at investigator discretion.
- ^c Histological results will be documented for subjects who have had a prior liver biopsy.
- ^d For subjects receiving rescue open-label ETV to treat an extreme elevation of ALT due to acute exacerbation of CHB only.
- ^e Adverse events should be recorded at week 6 for all subjects enrolled in LTFU, and at each visit for subjects receiving rescue open-label ETV.
- ^f Volume of blood to be collected may vary based on available specimen collection tubes.
- ^g While on study treatment.
- ^h WOCBP only. Additional home pregnancy testing will be required in between study visits starting from Week 18 and every 12 weeks thereafter while on study treatment.
- ⁱ All subjects enrolled in LTFU should undergo pregnancy testing at week 6. Subjects receiving rescue open-label ETV should be tested every 6 weeks during treatment and 6 weeks after the last dose of study medication (home pregnancy tests should be used in between study visits).
- ^j For subjects still on study ETV only (Section 6.9.2).

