6.3.2 Adverse Event Monitoring

Subjects will be closely monitored throughout the study for adverse events. Subjects who have study medication completed or discontinued permanently must be followed for the full 5 years of the study.

During the dosing phase, palatability issues with respect to the oral solution (placebo or active drug) should be reported as Adverse Events.

During the observational long-term follow up phase, Adverse Events related to the administration or discontinuation of study drug should be documented for subjects that are not receiving commercially available anti-HBV therapy. Serious Adverse Events and HBV-related diagnoses should be reported during the long-term follow up phase, regardless of whether or not the subjects are receiving commercially available anti-HBV therapy.

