7.3.3 Nonserious Adverse Events

The collection of nonserious AE information should begin at initiation of study drug. Nonserious AE information should also be collected from the start of a placebo lead-in period or other observational period intended to establish a baseline status for the subjects. During the long-term follow up phase, Adverse Events related to the administration or discontinuation of study drug should be documented for subjects that are not receiving commercially available anti-HBV therapy. Also during the LTFU phase, all adverse events should be documented in subjects receiving rescue open-label ETV.

If an ongoing nonserious AE worsens in its intensity or its relationship to the study drug changes, a new nonserious AE entry for the event should be completed. Nonserious AEs should be followed to resolution or stabilization, or reported as SAEs if they become serious (see Section 7.3.1). Follow-up is also required for nonserious AEs that cause interruption or discontinuation of study drug, or those that are present at the end of study treatment as appropriate.

All identified nonserious AEs must be recorded and described on the appropriate nonserious AE page of the CRF (paper or electronic).

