### 6.3 Populations for Analyses

- **Enrolled subjects** are those who sign an informed consent form and are assigned a Patient Identification number (PID). This cohort is used to assess subject disposition, deaths and serious adverse events during the **pre-treatment period**.
- **Randomized subjects** are enrolled subjects who receive a treatment assignment from the central randomization center. This cohort is used to assess subject status and accrual.
- **Treated subjects** are randomized subjects who receive at least 1 dose of study therapy. This cohort is used to assess all data domains.
  - **Primary cohort** is defined as at least the first 123 subjects randomized and treated. The Primary Cohort is used for the primary analyses.
- **Off-treatment follow-up subjects** are treated subjects who discontinue study therapy and have at least 1 of the following assessments during the **off-treatment follow-up period** (see [Section 6.1](#)): death date if it exists; adverse event onset date; HBV related diagnosis date; vital signs date; physical measurement date; physical exam date; neurologic exam date; laboratory test date (safety, pregnancy, serology and virology); liver biopsy date; Tanner staging date. This cohort is used to assess safety during the off-treatment follow-up period.
- **Long-term follow-up subjects** are treated subjects who discontinue study therapy and have at least 1 of the following assessments during the **long-term follow-up period** (see [Section 6.1](#)): death date if it exists; adverse event onset date; HBV related diagnosis date; vital signs date; physical measurement date; physical exam date; neurologic exam date; laboratory test date (safety, pregnancy, serology and virology); liver biopsy date; Tanner staging date. This cohort is used to assess safety during the long-term follow-up period.
- **Alternative ETV follow-up subjects** are treated subjects who discontinue study therapy, receive at least 1 dose of alternative ETV therapy, and have at least 1 of the following assessments during the **alternative ETV follow-up period** (see [Section 6.1](#)): death date if it exists; adverse event onset date; HBV related diagnosis date; vital signs date; physical measurement date; physical exam date; neurologic exam date; laboratory test date (safety, pregnancy, serology and virology); liver biopsy date; Tanner staging date. This cohort is used to assess safety during the alternative ETV follow-up period.

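### SAP 7.6.4.1 takes HBV disease progression only from AE terms, so a non-serious progression diagnosis made in long-term follow-up may go uncounted

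*SAP*

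**What the plan says.** SAP 7.6.4.1 summarizes progression events by regimen in treated subjects "across the on-treatment and long-term follow-up periods combined". The only definition of an event is Table 7.6.4.1-1, a list of ten terms under the label "Serious and non-serious AEs: preferred terms in MedDRA dictionary". SAP 7.6.8 repeats the endpoint, over the same combined periods, in the subgroup tables.

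The protocol collects a second item in LTFU. The flow chart in Protocol 6.1 has a row "Assess HBV related diagnoses", marked in the LTFU column only and separate from the AE and SAE rows. Protocol 6.3.2 states: "Serious Adverse Events and HBV-related diagnoses should be reported during the long-term follow up phase", and this applies whether or not the child takes commercial anti-HBV therapy.

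Non-serious AE collection in LTFU is narrower. Protocol 6.3.2 says: "Adverse Events related to the administration or discontinuation of study drug should be documented for subjects that are not receiving commercially available anti-HBV therapy". Protocol 7.3.3 repeats this and adds that children on rescue open-label entecavir have all AEs documented. Footnote e of the flow chart puts it differently: "Adverse events should be recorded at week 6 for all subjects enrolled in LTFU", and at every visit for those on rescue entecavir.

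The SAP handles the diagnosis as its own data item. Section 6.3 lists "adverse event onset date; HBV related diagnosis date" as two separate entries when it defines who has follow-up data, and section 8.9 lists the diagnosis separately again when it derives the last contact date.

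**The concern.** The table covers a period in which AE recording is restricted, yet it relies on AE records alone. The item that the protocol collects in every child to pick up HBV-related disease in that period is not used as an outcome anywhere in the SAP. It serves only to establish cohort membership and last contact, and through last contact the time in follow-up (SAP 7.4.1).

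What is at stake is the long-term safety description. Evaluating long-term safety is a stated secondary objective, and this table is where a reader would look for progression over five years. An omitted source can only lower the count.

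**Working it through.** The documents give no progression rate or event count, so there is no plan figure to reproduce. The check is a trace through the passages, plus visit arithmetic.

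**Trace of one event.** Take a non-serious diagnosis of non-bleeding varices, made at LTFU Week 48 and judged unrelated to study drug, in a child not on rescue entecavir.

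1. SAE record: not required, because the event is non-serious.
2. AE record under Protocol 6.3.2 and 7.3.3: not required, because the event is not related to giving or stopping study drug. If the child takes commercial anti-HBV therapy, it falls outside the rule on that ground too.
3. AE record under footnote e: not required, because the visit is not Week 6.
4. HBV-related diagnosis record: required under 6.3.2.
5. Table 7.6.4.1-1: not counted unless the site also entered the event as an AE or SAE.

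The flow-chart row for HBV-related diagnoses refers to Protocol 7.3. Sections 7.3 to 7.3.3 contain no instruction to copy these diagnoses into AE records.

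**Which listed terms are exposed.** Four of the ten can plausibly be non-serious: hepatic cirrhosis, gastric varices, oesophageal varices and ascites. The other six are the two variceal haemorrhage terms, encephalopathy, hepatorenal syndrome, bacterial peritonitis and malignant hepatic neoplasm. The first five of these would ordinarily meet an SAE criterion, and Protocol 7.1.1 sends cancer to an SAE form in any case.

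**Time under restricted recording.** Inputs are a total of 264 weeks (Protocol 4.1), dosing that ends at Week 96, 144 or 192 (Protocol 4.1 and 4.1.1), and LTFU visits at Weeks 6, 12 and then every 12 weeks. LTFU weeks = 264 − end of dosing. Visits = 1 + LTFU weeks/12.

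| End of dosing | LTFU weeks | Share of 264 | Visits assessing HBV diagnoses | Visits recording AEs (flow chart, no rescue) |
|---|---|---|---|---|
| Week 96 | 168 | 64% | 15 | 1 |
| Week 144 | 120 | 45% | 11 | 1 |
| Week 192 | 72 | 27% | 7 | 1 |

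**Illustration only.** Assume that events are spread evenly over the 264 weeks, and that a share q of LTFU events is non-serious and never entered as an AE. The missed share of all events is then (LTFU share) × q. With q from 0 to 0.75:

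- 72 weeks of LTFU: 0.273 × 0 to 0.273 × 0.75, or 0 to 20%.
- 168 weeks of LTFU: 0.636 × 0 to 0.636 × 0.75, or 0 to 48%.

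The value of q is an assumption, and zero is within its range.

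**By arm.** A child who does not seroconvert and completes scheduled dosing stops at Week 96 if randomized to entecavir. If randomized to placebo, the child stops at about Week 144 (48 weeks of placebo plus up to 96 of entecavir). Time in LTFU is then 168 against about 120 weeks, so any loss need not be balanced between the regimens compared.

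**The case against.** The strongest reply is that a separate date in the SAP does not prove the event is absent from the AE data. Protocol 6.3.2 sits under the adverse event heading, the flow-chart row refers to the AE reporting section, and sites may enter the diagnosis both ways. The CRF, its completion guidelines and the Data Presentation Plan are not available here. This stands as a limit: the loss is possible under the plan as written, but not demonstrated.

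Second, AE recording in LTFU is not closed. Events related to stopping study drug are collected, which could cover post-treatment worsening. So are AEs at LTFU Week 6, and all AEs on rescue entecavir, which is reserved for children with extreme ALT exacerbations. Protocol 7.3.1 also asks for an SAE report whenever seriousness is in doubt. A reader might infer that every non-serious, unrelated diagnosis in LTFU is lost; these provisions show that this goes too far.

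Third, the endpoint in Protocol 8.3 and SAP 4.3 is progression through Week 48. During treatment AEs are assessed at every scheduled visit, and the diagnosis row is not marked there, so no second source is being ignored. A reader might infer that the secondary endpoint is compromised. It is not, apart from children who stop before Week 48 and enter follow-up early.

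Fourth, the table is descriptive and carries no hypothesis test. Protocol 4.2.2 also excludes children with current or past variceal bleeding, encephalopathy or ascites requiring diuretics or paracentesis. That limits the consequence but leaves the gap open. With few events, one or two omissions would change the picture.

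**Conclusion.** The gap is real but limited. As written, SAP 7.6.4.1 may undercount progression in the combined treatment and LTFU summary, because it leaves out a source that the protocol collects in all children. The exposed events are non-serious ones, judged unrelated to study drug, in children not on rescue entecavir, and realistically fall under four of the ten listed terms.

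The documents do not give the size. The 64% figure is a share of time for a course ending at Week 96 and should not be read as a share of events; 45% and 27% apply to the later end dates. The 0 to 48% illustration rests on the assumed q and on even spread of events over time. The conclusion rests on one further assumption: that sites follow the LTFU collection rules as written and do not routinely enter these diagnoses as AEs as well. The through-Week-48 endpoint is largely unaffected, and serious events and cancers remain captured.

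**What to change.** In SAP 7.6.4.1, define a progression event as either a listed preferred term from AE or SAE records, or a matching HBV-related diagnosis record coded to the same terms. Count each subject once, at the earliest date, and show which source supplied the event. Present events through Week 48 and on treatment separately from LTFU events, so that the protocol endpoint can be read on its own. Carry the same definition into the subgroup tables of SAP 7.6.8. SAP 7.6.1 already identifies deaths from several sources, so the approach is not new to the plan.

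The cost is coding of an item already collected, a rule against double counting, and one revised table with its subgroup versions. No new data collection is needed. If the CRF guidelines already require these diagnoses to be entered as AEs, a sentence in the SAP saying so would close the gap in the count.
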